adjusted for in the *a* and *b*-path analyses. Mediators in the final mediator model will be selected using a backward selection approach.¹¹² We will also compute and compare proportions of mediated effects along with their standard errors across the single and multiple mediator models, as well as across time points where the mediators are measured.¹¹³ A larger proportion of the mediated effect in general suggests a larger mediation effect. Additional mediation analysis for repeated measures abstinence analyses will be conducted using a similar approach with both *a* and *b* paths involving repeated measures analysis, as applicable.¹¹³

Missing Data and Dropouts. It is anticipated that some individuals will drop out or be lost to follow-up, as is typical in smoking cessation treatment studies. Our primary analysis for examining abstinence at 18 months will utilize an intent-to-treat approach by coding missing abstinence data as smoking. However, we will also conduct sensitivity analyses by examining alternative approaches for handling missing data, including multiple imputation (under a missing at random assumption),^{114,115} and selection models (under an assumption of non-ignorable missingness, or missing not at random).^{114,116-118} In the multiple imputation approach, we will conduct analyses to examine whether participants who drop out of the study differ from those who do not, and include those covariates in our multiple imputation models, to mitigate the potential impact of non-ignorable missingness. Regardless of the approach used to handle missing data, it is unlikely that serious biases in estimation or considerable loss of efficiency in inference will result when the proportion of missing data low (e.g., not more than 10%; even more so when the missing data proportions are similar in MAPS and ST).

Overall, robust results based on both the primary and sensitivity analyses will strengthen our study findings.

Power. Our power analysis is based primarily on the comparison of 18-month abstinence rates between MAPS and ST. Because an intent-to-treat approach will be used, power is calculated based on the full sample without attrition (N=300; 150 per group), given that individuals lost to follow-up will be treated as smoking). All power analyses assume a significance level of 0.05 and a two-sided test. Based on the *Guideline*,²⁰ we estimated that abstinence for ST would be approximately 10%. Using a chi-square test to examine the effect of treatment on abstinence at 18 months, a sample size of 300 (150 per group) will provide 80% power to detect an overall treatment effect that corresponds to abstinence rates of 10% and 21.9% in ST and MAPS respectively. Relative to examining abstinence over time, these calculations represent the worst case scenario. Table 2 presents detectable differences across a range of possible abstinence rates. Analyses conducted using GLMM will have greater power to detect the same average differences across time.

Table 2. Detectable differences in binary smoking outcomes with 80% power (abstinence, quit attempt)	
ST (n=150)	MAPS (n=150)
5.0%	14.60%
10.0%	21.90%
20.0%	34.40%
30.0%	45.70%
40.0%	56.20%

Although the proposed mediation analyses for aim 2 are theoretically-grounded and hypothesis-driven (see Figure 1), they are quasi-exploratory in nature, and the sample size for this study was based on power to detect a significant difference for Aim 1. Nonetheless, power for the mediation analyses (Aim 2) has been calculated as follows. For the mechanism analyses (Aim 2), power is based on a conservative 25% attrition rate (N= 300; 112 per group). Because the mechanism variables are continuous, a sample size of 300 (112 per group at 18 months) will provide 80% power to detect an effect size of 0.376 standard deviation (SD) unit (difference in means between the ST and MAPS divided by common SD), using a two group t-test with a 0.05 two-sided significance level. Because we have excellent power to detect treatment effects on the primary outcome and mechanisms, as well as the effects of mechanisms on abstinence (with power generally greater using continuous predictors than binary predictors such as treatment group), we expect to have good power to detect mediation effects. We note, however, that the power calculated for analyses in Aim 2 should be considered in the context of inflated type 1 error due to multiple analyses and hypothesis tests (including the mediation analyses) being performed for this aim. We feel that this inflated type 1 error is acceptable given the quasi-exploratory nature of this aim. Nevertheless, future studies focusing on testing specified mediational models should be sufficiently powered using approaches of Fritz and MacKinnon¹¹⁹ or Thoemmes et al.¹²⁰, as appropriate.

Cost Effectiveness

Methods overview. Cost-effectiveness analyses (CEA) will compare the two interventions: ST and MAPS. The conventional CEA summarizes study findings in terms of the incremental cost-effectiveness ratio (ICER).^{121,122} The ICER, calculated as the difference in mean costs between the new and standard treatment divided by the difference in mean effectiveness between the new and standard treatment, estimates the additional resource consumption needed to achieve an increase in an additional unit of effectiveness. The ICER is then compared with a commonly cited or published threshold value associated with an intervention already found to be cost-effective to determine whether a new intervention is cost-effective.

The net benefit approach, introduced more recently,^{123,124} transforms the ICER into the net benefit, defined as $NB(\lambda) = \lambda \cdot \Delta E - \Delta C$, where λ represents a societal willingness-to-pay (WTP), ΔC represents the incremental costs; and ΔE represents the incremental effectiveness. We will report the CEA results both in terms of the conventional ICER and the CE acceptability curve,^{123,125} the latter informs decision makers of the probability that the new intervention is more cost-effective than the standard treatment at various levels of societal WTP. The net benefit approach has been incorporated into a regression framework to allow for covariate adjustments and examination of interaction effects in CEA.¹²⁶ Shih and colleagues further extended this net benefit regression framework to a Bayesian regression framework to allow the inclusion of prior knowledge and more flexible inferences.^{127,128} This regression-based approach is relevant to our study as there may be moderating factors such as individual characteristics that affect the cost-effectiveness of interventions.

Measures of costs and collection of cost data. For each of the two intervention arms, the costs associated with implementing the intervention will come from three sources: study personnel, production of materials, and materials to participants. Project staff will keep logs of time spent on each of the tasks related to implementing the intervention, net of additional time that may be spent to satisfy the research and evaluation components of the project. Costs of developing training materials and information systems will apply to each intervention arm, whereas costs associated with training counselors will apply only to MAPS. Any hardware costs necessary for implementing the intervention will be tracked through invoices. Material costs will be obtained from invoices maintained by project staff from vendors delivering intervention materials. All intervention-related costs will be expressed in local market terms for personnel, office space, furnishings, and equipment. The cost model will include all personnel, hardware, and material costs necessary to implement the interventions. Even if the research team uses existing resources at Moffitt Cancer Center, Stephenson Cancer Center, or the quitlines without charge (e.g., office space, phones, computers), we will estimate all of the expenses necessary for implementing MAPS since these expenses would be required for the implementation of population-based tobacco control programs. We will not include other health care costs. This decision was based on the existing evidence regarding the health care cost consequences associated with smoking and cessation and the expectation of how this evidence impacts the difference in costs among different intervention arms. Although smokers incur greater health care costs than non-smokers,¹²⁹⁻¹³³ it has been shown that cost savings related to improvement in health from cessation may be balanced out by future cost increases due to greater longevity.¹³⁴ In addition, former smokers incur greater short-term health care utilization and costs than continuing smokers.^{132,135} That increase in cost however, is likely linked to a health event that precedes and motivates the successful quit attempt. That is, higher health care costs are concurrent with but not caused by smoking cessation.

Measures of Effectiveness. Two commonly used effectiveness measures in studies comparing the cost-effectiveness of cessation interventions are number of quitters and years of life saved (YOLS).¹³⁶ To facilitate comparing ICER estimated from our CEA with that from other published studies, we will include both measures. The number of quitters in each treatment arm will be retrieved from the primary abstinence endpoint at month 18. We will extrapolate from abstinence to YOLS using a published algorithm that models YOLS per quitter for persons in various age-specific subgroups.¹³⁷ In addition, to assist decision making in selecting among interventions targeted at different conditions that compete for limited budgets, we also included quality-adjusted life year (QALY) as an additional effectiveness measure, and calculate QALY from the health utilities obtained from the EQ-5D. This algorithm was favored over other published methods of extrapolation because it was built from a model with good face validity and has been adopted in many related CE studies.¹³⁶

Analysis. We will compare the cost-effectiveness of the interventions in three time frames: short-term, mid-term and long-term. The short-term and mid-term CEA will use "number of quitters" as the effectiveness measure and assess cost-effectiveness based on information collected at Months 3 and 6 (short-term), Month 12 (mid-term), and month 18 (long-term), respectively. The long-term analysis will extrapolate the intervention effect to lifetime and use YOLS and QALY as the effectiveness measure. A 3% discount rate will be applied to costs and outcomes accrued in the second year and forward. First, we will work with the lead biostatistician of

this study ([name]) to address the issue of missing data using analytical approaches such as multiple imputation or selection models (details see above) and obtain imputed values for individual with missing value in cost and/or effectiveness variable. Next, we will perform deterministic CEA based on ICER. We will then apply the Bayesian approach to construct the CE acceptability curve and conduct probabilistic sensitivity analysis (PSA).^{138,139} The PSA assigns distributions for each of the key parameters to characterize uncertainties in each parameter, propagates all parameter uncertainties through the model simultaneously using simulation methods, and generates an empirical distribution for either the ICER or the net benefit.^{140,141} it has been incorporated in more recent CEA *Guidelines*.¹⁴² We will conduct the Bayesian analysis using WinBUGS, with costs modeled as a gamma or lognormal distribution and abstinence from tobacco or as a binomial distribution.

Finally, we will apply the regression-based cost-effectiveness analysis. Individual-level net benefit will be regressed on covariates, plus a binary variable indicating the ST vs. MAPS arm. Using the "ST" arm as the reference group, the regression coefficients associated with the treatment binary variable will provide information on the cost-effectiveness of the MAPS intervention compared to ST. The regression model will be analyzed in two ways: 1) GLMM to examine how cost-effectiveness varies over time, and 2) Bayesian regression to systematically update information gathered at each time point.

Table 3. Project Phases and Timeline	
Phase 1: 1 Year	Refinement of Treatment Manuals, Counselor Training, Data Management and Tracking Systems, Focus Groups, Pilot Testing
Phase 2: 3.5 Years	Enroll 300 participants, Implement Procedures (Recruitment, Screening, Randomization, Treatment Delivery, Assessment, etc.)
Phase 3: 0.5 Years	Complete Data Analysis and Prepare Manuscripts for Publication

REFERENCES

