Stress/Negative Affect. Stress and negative affect, measured in many different ways, predict cessation outcomes. Affective predictors include affective responses to smoking-related acute events, individual differences in affective vulnerability, depressive symptoms, and the magnitude and trajectory of stress/negative affect over time.^{19,81,87,93-97} In addition to the stress/negative affect engendered by cessation, life stressors such as those experienced by cervical cancer survivors, have been shown to have adverse effects over time on motivation, self-efficacy, and abstinence.^{98,99} Further, social cognitive theory posits that weak motivation for abstinence can increase stress/negative affect, particularly during high-risk situations.²¹ Thus, MAPS is hypothesized to reduce stress/negative affect via its impact on decreasing ambivalence and increasing motivation, through the application of coping skills training and problem-solving, and through utilization of a holistic approach in which other life concerns and stressors are addressed.

APPROACH

Project Design and Procedures. Participants will be women with a diagnosis of cervical cancer or high grade cervical dysplasia who report smoking any cigarettes within the past 30 days, recruited through the Stephenson Cancer Center or OU Physicians at the University of Oklahoma Health Sciences Center, via the ClinicalTrials.gov website, by responding to recruitment flyers and internet advertisements (e.g., flyers in clinics, Facebook), and through referrals from healthcare providers. Participants will be followed for a period of 18 months, and randomly assigned to one of two groups: 1) Standard Treatment [ST], or 2) Motivation and Problem Solving [MAPS]. ST will consist of a mailed packet of materials including a letter referring smokers to the Oklahoma Tobacco Helpline, Florida Quitline or to the national quitline number ([name]) for participants residing in other states, free nicotine replacement therapy when they are ready to quit, and standard self-help materials. ST will be mailed a total of 3 times to participants with completed assessments (at Baseline, 6 and 12 months). MAPS will consist of ST plus up to 6 proactive phone counseling sessions delivered over a 12-month period. The timing of counseling sessions in MAPS is flexible and determined jointly by the participant and the counselor.

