Assessment calls will occur at Baseline and at 3, 6, 12, and 18 months after Baseline. The primary outcomes are abstinence from tobacco at the 18-month follow-up and abstinence across all follow-ups. Secondary outcomes are smoking quit attempts, cigarettes per day, use of the quitline, and cost-effectiveness. Participants will be scheduled to complete a baseline assessment call within one week. Following the baseline assessment, participants will be randomly assigned to ST or MAPS. Participants will schedule their first counseling call at that time (see Table 1).

Recruitment. Participants will be women with a diagnosis of cervical cancer or high grade cervical dysplasia who report smoking any cigarettes within the past 30 days, recruited through the Stephenson Cancer Center or OU Physicians at the University of Oklahoma Health Sciences Center, via the ClinicalTrials.gov website, by responding to recruitment flyers and internet advertisements (e.g., flyers in clinics, Facebook), and through referrals from healthcare providers.

Participant Eligibility. Inclusion criteria: ≥ 18 ; current smoker with a history of at least 100 lifetime cigarettes and a self-report of smoking within the last 30 days; history of cervical cancer or high grade cervical dysplasia (we have defined survivorship as beginning at the time of cancer diagnosis, consistent with the NCI definition); has a working cell phone; valid home address; speaks English, Spanish or both languages. Exclusion criteria: current use of tobacco cessation medications; self-report of being pregnant or lactating; or, another household member enrolled in the study; or contraindication of nicotine patch use unless under the supervision of a physician as advised by project staff.

Table 1. Schedule of Study Procedures and Assessments	Screening	Baseline	Month 3	Month 6	Month 12	Month 18
Inclusion/Exclusion Criteria	X	X				
Compensation		\$60	\$60	\$60	\$60	\$60
TREATMENT PROCEDURES						
Standard Treatment (ST)	Delivered at Baseline, and Months 6 and 12					
Motivation And Problem Solving (MAPS)	ST plus up to 6 MAPS Counseling Calls delivered over 12 months					
DEMOGRAPHICS, MENTAL HEALTH						
Demographics and Smoking History		X				
Cancer stage at diagnosis, time since diagnosis, current stage, treatment status	X					
Subjective Social Status		X	X	X	X	X
Fear of Cancer Recurrence Inventory (FCRI)	X	X	X	X	X	X
MOTIVATION						
Contemplation Ladder		X	X	X	X	X

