Reasons for Quitting (Intrinsic and Extrinsic Motivation)		X	X	X	X	X
Motivation		X	X	X	X	X
AGENCY: SENSE OF CONTROL, SELF-EFFICACY, COPING BEHAVIOR						
Sense of Control		X	X	X	X	X
Self-Efficacy Scale		X	X	X	X	X
Coping Inventory		X	X	X	X	X
STRESS, NEGATIVE AFFECT						
Perceived Stress Scale (PSS)		X	X	X	X	X
Positive and Negative Affect Scale (PANAS)		X	X	X	X	X
Depression (CES-D)		X	X	X	X	X
SMOKING-RELATED MEASURES						
Heaviness of Smoking Index (HSI)		X	X	X	X	X
Wisconsin Smoking Withdrawal Scale (WSWS)		X	X	X	X	X
Wisconsin Inventory of Smoking Dependence Motives (WISDM-37)		X	X	X	X	X
SMOKING STATUS, BIOCHEMICAL VERIFICATION, QUITLINE USE						
Smoking Status (SRNT)	X	X	X	X	X	X
Use of the Quitline Cessation Services (including Pharmacotherapy)		X	X	X	X	X
Cotinine (only among participants reporting abstinence)			X	X	X	X
PATIENT REPORTED OUTCOMES						

Functional Assessment of Cancer Therapy – Cervix Cancer (FACT-Cx)	x	x	x	x	x	x
EQ-5D (for health utilities)		x	x	x	x	x

Screening and Informed Consent Procedures. After being screened in-clinic or completing a secure online screener via REDCap, potential participants will be contacted by research staff at Moffitt Cancer Center or Stephenson Cancer Center. All eligible individuals will be invited to participate. A detailed description of the study will be provided and informed consent will be obtained. For those who agree to enroll in the study, research staff will obtain informed consent either in-person or over the phone. When participants are consented over the phone, research staff will read the informed consent document to participants and will document in our database that verbal informed consent has been obtained. A copy of the informed consent document and project materials will be provided to participants either in-person or by mail. All informed consent materials will be available in both English and Spanish. Women who decline or are ineligible will be given self-help materials and a referral to other cessation programs if they so desire.

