Assessments. Research Electronic Data Capture (REDCap) will be used to administer all questionnaires over the phone, in person, and/or via a web-based link when convenient for the participant. REDCap is a secure, web-based application designed to support data capture and utilizes a computer-administered self-interview format. This system is used in all of our current research and is designed to comply with all HIPAA regulations. Having research staff read the questionnaire items to participants will help overcome problems related to low literacy levels. Finally, we will attempt to reduce the inconvenience associated with completing assessments by providing financial compensation for participants' time. In sum, the battery of instruments comprehensively assesses our hypothesized mechanisms and associated variables of interest. A copy of each assessment instrument is included in the Appendix and all measures are listed in the Procedures Table (Table 1).

Smoking Abstinence. Abstinence assessments are based on recommendations from the Society for Research on Nicotine and Tobacco (SRNT).¹⁰⁵ We will report both prolonged and point-prevalence abstinence

at all follow-up assessment points. Prolonged abstinence refers to abstinence beginning with the initiation of treatment and including a grace period. The prolonged abstinence measure utilizes SRNT's recommendation for determining relapse (i.e., 7 consecutive days of smoking or smoking in each of 2 consecutive weeks). We will also evaluate two point-prevalence abstinence measures: 1) no smoking during the previous 7 days, and 2) no smoking during the previous 30 days. For all abstinence measures, we will analyze both completers only, and intent to treat in which smokers lost to follow-up are considered smoking. Abstinence at all follow-ups will be biochemically verified using a saliva cotinine level of <20 ng/ml.

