Participants who self-report abstinence will be mailed a prepaid envelope, instructions for providing the cotinine sample, and a saliva cotinine kit. Research staff will contact participants by phone to ensure the arrival of packet, review the contents of the packet, and answer any questions participants may have about collecting a saliva specimen. Although cotinine cannot comprehensively validate the various abstinence definitions and timeframes, the most comprehensive review on biochemical validation concluded that misreporting is typically very low (~2%), and that adjustment for misreporting almost never influences analyses regarding relative treatment efficacy.¹⁰⁶ As such, our biochemical validation procedures are well justified both scientifically and practically.

PSYCHOLOGICAL DISTRESS ASSESSMENT AND MANAGEMENT PLAN

If a participant: 1) states that she is thinking about harming herself or others, or 2) uses actions or words to lead us to believe that she may be in eminent danger or in danger of harming another person, research staff will execute our standard crisis procedures. These procedures are described in detail in Appendix H. Once the plan is executed, a trained counselor will assess the participant using the "Crisis Assessment" (Appendix I). Participants will also be encouraged to follow ups with a mental health professional of their choice. Our team will have extensive interactions with participants throughout the course of the study. Therefore, our plan is appropriate for our target population.

STATISTICAL CONSIDERATIONS

Data Analysis Approach. The primary outcome is abstinence from smoking at the 18-month assessment. To test the treatment effect at 18 months, we will conduct logistic regression analysis with abstinence as the outcome variable, and treatment (a two-level categorical variable) as the predictor, adjusting for covariates, specifically, factors used in the minimization procedures (race/ethnicity, language, age, education, income, cigarettes/day, cervical cancer stage, and time since diagnosis). Interactions between treatment and specific covariates of interest may be included and tested for exploratory purposes.

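### Women already abstinent for 7 days at baseline can be enrolled, and baseline 7-day smoking status, likely a strong predictor of the outcome, is missing from the listed covariates

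*Combined protocol and SAP*

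**What the plan says.** Project Design and Procedures and Recruitment (both under APPROACH) describe participants as women "who report smoking any cigarettes within the past 30 days". Participant Eligibility asks for a "current smoker with a history of at least 100 lifetime cigarettes and a self-report of smoking within the last 30 days". No criterion requires smoking in the past 7 days, daily smoking or a minimum rate. One exclusion removes some recent quitters: "Exclusion criteria: current use of tobacco cessation medications". Table 1 marks the eligibility criteria at both screening and baseline, and the gap between the two is short: "Participants will be scheduled to complete a baseline assessment call within one week".

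Under Data Analysis Approach, "The primary outcome is abstinence from smoking at the 18-month assessment". The Smoking Abstinence section lists three measures and does not say which one is primary: prolonged abstinence (from the start of treatment, after a grace period), 7-day point prevalence ("no smoking during the previous 7 days") and 30-day point prevalence.

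Table 1 has a smoking-status row, marked at screening, baseline and every follow-up. The 18-month logistic model adjusts for "factors used in the minimization procedures (race/ethnicity, language, age, education, income, cigarettes/day, cervical cancer stage, and time since diagnosis"). The minimization list under Baseline Assessment and Randomization differs somewhat from that list. Cigarettes/day is in both; baseline abstinence is in neither. The repeated-measures model (GLMM) leaves its covariates open.

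**The concern.** The entry window (30 days) is wider than one outcome window (7 days). A woman can be an outcome success on the 7-day measure on the day she is randomized, and if she stays quit she is a success at 18 months. Recent quitters are likely to have a much better chance of being abstinent later than women who are still smoking. Baseline status is therefore likely to be strongly prognostic, and leaving it out of the model gives up precision that the trial's own data could supply. Cigarettes/day does not clearly replace it: the plan gives that item no recall window, and a usual-rate answer does not show whether a woman smoked in the last week.

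There is also a matter of description. The Cost Effectiveness section takes the number of quitters from month-18 abstinence and extrapolates it to years of life saved. The count in each arm would include women who had stopped before randomization.

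**Working it through.** **1. Which measures overlap with entry.** Take a woman whose last cigarette was 8 to 30 days before baseline and who uses no cessation medication.
- 7-day point prevalence: already met at baseline.
- Prolonged abstinence: counted from the start of treatment, so continued abstinence is credited.
- 30-day point prevalence: almost no overlap. It could arise only if the criterion were applied at screening and not again at the baseline call up to a week later.

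**2. The plan's own power figure.** Inputs from the Power section: 150 per arm, 10% vs 21.9%, two-sided 0.05, chi-square test. The uncorrected test gives 80.7% power, and 148 per arm are needed for 80%. The stated 80% reproduces and is not in dispute.

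**3. Share of ST abstainers.** Assumptions, not in the documents: a share f = 5-15% is 7-day abstinent at baseline, and a proportion q = 30-40% of them is abstinent at 18 months under ST. The overall ST rate is held at the plan's 10%.
- Share of ST abstainers = f × q / 0.10. Lowest: 0.05 × 0.30 / 0.10 = 15%. Highest: 0.15 × 0.40 / 0.10 = 60%. At f = 10% it is 30-40%.
- Implied ST rate in the other women = (0.10 − f × q) / (1 − f). Lowest case: 0.085 / 0.95 = 8.9%. Highest case: 0.040 / 0.85 = 4.7%.

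**4. Chance imbalance.** One SD of the between-arm difference in share is √(2f(1 − f)/150). Multiplying by the gap in abstinence gives the shift in the arm difference:
- f = 5%, q = 30%: 0.0252 × (0.300 − 0.0895) = 0.53 points.
- f = 15%, q = 40%: 0.0412 × (0.400 − 0.0471) = 1.46 points.

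For scale, the standard error of the arm difference is √(0.10 × 0.90/150 + 0.219 × 0.781/150) = 4.2 points. The imbalance is part of that error and does not come on top of it.

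**5. What adjustment buys.** Trials of 150 per arm were simulated with marginal rates held at 10% and 21.9% and a common odds ratio within baseline-status groups. A logistic model with treatment only was compared with one that adds baseline status. The other planned covariates were not simulated.

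| f | q | Power, treatment only | Gain from adjusting |
|---|---|---|---|
| 5% | 30% | about 81% | about 1 point |
| 10% | 30% | about 81% | about 1-2 points |
| 10% | 40% | about 81% | about 4 points |
| 15% | 40% | about 81% | about 8 points |

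**6. Power of an estimate among baseline smokers only.** Assuming 10% vs 21.9% in that group: 150 × 0.95 ≈ 142 per arm gives 78.5%, and 150 × 0.90 = 135 per arm gives 76.4%.

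**The case against.** The strongest reply is that sustained abstinence is something the intervention is meant to produce. The SIGNIFICANCE section speaks of preventing relapse as well as quitting, MAPS is offered whatever the woman's readiness to change, and the Treatment Plan foresees calls for women struggling to stay quit. This stands. It is why these women belong in the primary analysis, and why confining the word cessation to a subgroup estimate would be a preference and not a correction.

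It also stands that any prognostic factor left out of a model behaves this way, that the gain is small unless such women are common, and that the documents do not say how common they are. The Table 1 row shows only a label, so the item wording has to be confirmed.

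A reader might infer four stronger things that the documents do not support:
- **That the comparison is biased.** Allocation is randomized, and cigarettes/day is both balanced and adjusted for. The effect is imprecision.
- **That the primary outcome is the affected measure.** The 7-day measure is one of three and none is named as primary. If the 30-day measure were primary, the overlap would nearly vanish.
- **That a woman who stays quit fails on the quit-attempt outcome.** The plan says only that this outcome is binary. It gives no definition, look-back period or scoring rule.
- **That power falls well below 80%.** Fixing the odds ratio at 2.52 within baseline-status groups gives unadjusted powers of about 75%, 67% and 58% in the last three scenarios of the table. But the MAPS rates are then only 21.0%, 20.0% and 18.8%, so most of the drop comes from assuming a smaller effect. Powers of 75-62% also arise at shares of 5-10% if 30-70% of these women are abstinent at 18 months in both arms, meaning MAPS does nothing for them. That contradicts its relapse-prevention purpose.

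**Conclusion.** The point holds as a minor one. Women abstinent for 8 to 30 days can be enrolled, already meet the 7-day measure at randomization, and can be credited on the prolonged measure. The plan collects the variable that identifies them but does not prespecify its use.

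On assumed shares of 5-15% and assumed ST abstinence of 30-40%, they supply 15-60% of ST abstainers, and adjustment adds about 1 to 8 points of power. The upper end needs extreme inputs: at 15% and 40%, the baseline odds ratio is (0.40/0.60)/(0.0471/0.9529) = 13.5. The practical gain is probably nearer the lower end, and baseline data would settle the share without any look at outcomes.

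The difference between arms in the number of quitters remains a valid randomized comparison. What is mixed is the count within each arm, which combines new cessation with maintained abstinence.

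**What to change.** Before any unblinded analysis:
1. Keep all randomized women in the primary analysis.
2. Add baseline 7-day smoking status (smoked or did not smoke in the 7 days before baseline) as a prespecified covariate in the 18-month logistic model and in the abstinence GLMM. Take it from the baseline smoking-status item, after confirming that the item records this.
3. Report one supportive 18-month estimate among women who smoked in the 7 days before baseline, and state its slightly lower power. Report the number abstinent at baseline in each arm.

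The cost is wording in the statistical section: no new data, no change to eligibility and no lost sample. The model gains one covariate, so its odds ratio is conditional on one more factor. If baseline data show almost no such women, the covariate changes little.
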